10.6.1.3 Dose Modifications for Progressive Multifocal Leukoencephalopathy (PML)

PML is a rare demyelinating disease of the brain that is caused by the John Cunningham virus (JCV). It typically occurs in immunocompromised individuals and can be fatal. Presenting features may include altered mental status, motor deficits such as hemiparesis or ataxia, visual disturbances, or higher cortical dysfunction such as dysphasia or agnosia. Seizures have also been reported in PML patients (approximately 20%). Cognitive decline without accompanying deficits in motor or sensory function is uncommon. Optic nerve involvement, fever, and spinal cord disease are not typically associated with PML. In addition, peripheral neuropathy, which has been reported with brentuximab vedotin treatment, is not commonly reported with PML.

If PML is suspected, a diagnostic work-up must be performed. The work-up may include, but is not limited to the following:

- Neurologic examinations and neurology consultation, as warranted
- Brain MRI. Features suggestive of PML include presence of unifocal or multifocal lesions, mainly of the white matter, which are typically non-enhancing and do not have mass effect.
- PCR analysis. JCV DNA, detectable in CSF or in a brain biopsy, is suggestive of PML.

• Brentuximab vedotin dosing must be held if PML is suspected. If PML is confirmed, brentuximab vedotin must be permanently discontinued.

10.6.1.4 Dose Modifications for Pulmonary Toxicity

Pulmonary toxicity will be defined by grade 3 or 4 dyspnea, pneumonitis, and/or hypoxia that persists for at least three days. There must be no evidence of other etiologies, including left atrial hypertension, congestive heart failure, infection, metabolic abnormalities, or cancer related causes (e.g., malignant pericarditis).

Patients who develop pulmonary toxicity associated with brentuximab vedotin may benefit from treatment with corticosteroids. However, there are no published guidelines to suggest the most appropriate dosing or duration of treatment. Administration of 100 mg of oral or intravenous prednisolone in single daily or two divided doses has been reported to improve symptoms in adults with pulmonary toxicity secondary to gemcitabine. The suggested dose for patients who develop pulmonary toxicity is methylprednisolone 1 mg/kg IV every 12 hours for a minimum of seven days. Patients who develop pulmonary toxicity meeting the above definition will be taken off protocol therapy.

See Section 13.1 for a complete listing of potential adverse events and Section 13.1.1 for special precautions and safety issues.

10.6.1.5 Dose Modifications for Febrile Neutropenia

For participants already dosed reduced for reasons other than febrile neutropenia (e.g., neuropathy), dose reduction must start from the level at which the febrile neutropenia occurs.

Treatment Modification Guidelines for AVD-Brentuximab Vedotin for All Cycles.

Episode of Febrile Neutropenia	Action
First Episode of Febrile Neutropenia	Maintain current brentuximab vedotin dose with quinolone prophylaxis, or reduce one dose level (investigator's discretion).
Second Episode of Febrile Neutropenia	Quinolone prophylaxis and reduce one dose level.
Third Episode of Febrile Neutropenia	Quinolone prophylaxis and reduce one dose level.
Fourth Episode of Febrile Neutropenia	Quinolone prophylaxis and reduce one dose level.

Dose Level	Brentuximab Vedotin	AVD
1	1.2 mg/kg	Full dose
-1	0.9 mg/kg	Full dose

-2	0.6 mg/kg	Full dose
-3	0	Full dose
-4	0	0.75

Quinolone prophylaxis: antibacterial therapy is required for all cycles after an initial episode of febrile neutropenia. Suggested regimen can be altered based on availability, allergies, or ANC trends (e.g., levofloxacin 750 mg PO daily, Days 6-13 and Days 20-27).

Participants who are unable to receive at least 4 doses of brentuximab vedotin will not receive further therapy on study.

See Section Error! Reference source not found. for a complete listing of potential adverse events and Section Error! Reference source not found. for special precautions and safety issues.

10.6.2 AVD-Brentuximab Vedotin Dose Modifications (applies to all cycles)

Hematologic Toxicity	Although it is common practice to attenuate doses or delay treatment due to cytopenias alone, recent studies have shown that in the non-HIV setting for cHL patients receiving delays results in suboptimal treatment outcomes ^{77,78} . Patients should receive full doses of AVD on schedule on Days 1 and 15 of each 28-day cycle without treatment delays, unless neutropenic fever or documented infections are present.
Febrile Neutropenia	If febrile neutropenia occurs, then prophylaxis with antibacterial therapy is recommended for the subsequent cycle (e.g., levofloxacin 500 mg PO daily, Days 6-13 and Days 20-27 unless neutropenia occurred earlier in the cycle). Continued antibacterial antibiotic use thereafter is at the discretion of the treating physician. If a second febrile neutropenia episode occurs, decrease the doses of vinblastine and doxorubicin to 75% of the previous dose received for the next cycle (in addition to above antibiotic and GCSF supportive care measures). Re-escalation is at the discretion of the treating physician. If a third episode of febrile neutropenia occurs, patients should be maintained on therapy with supportive measures unless infection is life threatening.
Transfusions	Erythrocyte and platelet transfusions will be administered as needed at the discretion of the treating physician.
Severe Infection	Severe infection (NCI CTC Version 5.0, Grade 3 or 4) due to chemotherapy- related neutropenia requires a decrease in the doses of vinblastine and doxorubicin to 75% of the last dose received for the next cycle. Re-escalation is at the discretion of the treating physician.

Impaired Hepatic Function	All patients with direct bilirubin ≤ 2 x the upper limit of normal (ULN) will receive a full initial dose of doxorubicin and vinblastine. If the direct bilirubin rises to ≥ 2 x ULN (but ≤ 5 x ULN), the doxorubicin and vinblastine doses must be reduced by 50% of last dose received to avoid undue hepatic toxicity. Full doses should be given once the direct bilirubin is ≤ 2 x ULN. If the direct bilirubin rises to ≥ 5 x ULN, doxorubicin and vinblastine should be discontinued for that cycle. If the direct bilirubin has not recovered to ≤ 2 x ULN by the time the next cycle is due, then remove patient from protocol treatment. In cases of obstruction of the biliary duct by a tumor mass, a biliary drainage stent should be placed prior to chemotherapy. Values must be within protocol eligibility at treatment initiation. Direct Bilirubin with appropriate Doxorubicin and Vinblastine Dose Adjustments ≤ 2 x ULN = 100% of last dose received
	> 2 - 5 x ULN = 50% of last dose received
	> 5 x ULN = discontinue (i.e., do not administer)
Neuropathy	Once brentuximab vedotin has been discontinued, patients experiencing Grade 3 vinblastine-neuropathy (e.g., obstipation, weakness) will have the dose of vinblastine reduced by 50% for all further cycles of AVD. Patients experiencing Grade 4 vinblastine neuropathy will have this drug omitted from all future cycles of AVD.
Pulmonary Toxicity	Every 2 cycles PFT will be performed. The DLCO adjusted for hemoglobin must be greater than 70% to continue with brentuximab vedotin.
Weight	If a subject's weight has changed more than 10% from baseline or the prior dose, the new BSA must be used on the next cycle. For a weight change of 10% or less, doses may be adjusted according to the BSA or remain the same in conjunction with institutional guidelines.

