5.2.2 Febrile Neutropenia

See Section 5.1.3 for AVD-brentuximab vedotin dose modification instructions for febrile neutropenia.

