	Grade 3-4	 Reinstitute growth factor support (GCSF) for treatment of neutropenia until recovery to ANC ≥1,000/mm3. If myeloid growth factor support was inadvertently omitted in the previous dose, patients should receive the same full dose of brentuximab vedotin in the next treatment dose, along with myeloid growth factor support If, as per protocol, the participant was on myeloid growth factor support with the previous dose and presents with treatment day neutropenia, reinstitute myeloid growth factor support (GCSF) until recovery to ANC ≥1,000/mm3 and reduce brentuximab vedotin one dose level for all remaining cycles. Dose reduction below brentuximab vedotin 0.6 mg/kg is not allowed. Brentuximab vedotin should not be given for any subsequent cycles. If participants have febrile neutropenia, please see Section 10.6 for dose modifications.
Thrombocytopenia	Grade 1-2	Continue at same dose level.
	Grade 3-4	 Withhold dose until toxicity is ≤ Grade 2 or has returned to baseline, then continue on protocol therapy but at one dose reduction Patients who experience Grade 3-4 thrombocytopenia after dose reduction must be removed from protocol therapy Patients who experience a delay of over 7 days in cycle 1 will be removed from the study. For subsequent cycles, if two sequential doses of brentuximab vedotin are held due to unresolved toxicity, leading to a treatment delay of an additional 2 weeks (i.e., 4 weeks between doses), the patient will be taken off protocol therapy.
Lymphopenia	Grade 1-4	Continue at same dose level.
Non-hematologic ^a events (not including electrolyte abnormalities) or febrile neutropenia) (See Section 10.6.1.5 for treatment modifications for febrile neutropenia)	Grade 1-2	Continue at same dose level.

Event	CTCAE.v4.0 Grade	Action to be Taken

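### French protocol: sections 10.6.1.5 and 10.6.2 prescribe different doxorubicin and vinblastine doses at the second febrile neutropenia episode

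*Combined protocol and SAP*

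**What the plan says.** **French protocol, 10.6.1.5 (Dose Modifications for Febrile Neutropenia).** Its tables are introduced as "Treatment Modification Guidelines for AVD-Brentuximab Vedotin for All Cycles".

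- First episode: "Maintain current brentuximab vedotin dose with quinolone prophylaxis, or reduce one dose level (investigator's discretion").
- Second, third and fourth episodes: "Quinolone prophylaxis and reduce one dose level".
- Participants already reduced for another reason: "dose reduction must start from the level at which the febrile neutropenia occurs".
- The level table has its own AVD column. AVD is at full dose at levels 1, -1, -2 and -3 (BV 1.2, 0.9, 0.6 and 0 mg/kg). It falls to 0.75 only at level -4, where BV is 0.

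**French protocol, 10.6.2.** This section is also headed as AVD-BV modifications for every cycle. At the second episode its febrile neutropenia row says to "decrease the doses of vinblastine and doxorubicin to 75% of the previous dose received for the next cycle", with re-escalation left to the treating physician. It states no change in BV and does not mention dacarbazine.

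**Cross-references in the table of 10.6.1.2.** The neutropenia row says "If participants have febrile neutropenia, please see Section 10.6 for dose modifications". The label of the non-hematologic row says "See Section 10.6.1.5 for treatment modifications for febrile neutropenia".

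**AMC protocol.** Section 5.1.3 has the same ladder. Section 5.2.2 has no rule of its own and only points to 5.1.3 "for AVD-brentuximab vedotin dose modification instructions for febrile neutropenia".

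**The concern.** One trigger, the second febrile neutropenia episode, leads to two different compulsory chemotherapy doses in the same protocol. One rule takes the reduction on BV and leaves AVD alone. The other takes it on doxorubicin and vinblastine and does not mention BV. A site that follows either one departs from the other, and no text settles which governs. At stake is whether a cytotoxic dosing instruction for a serious, foreseeable toxicity can be carried out consistently across the French sites.

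**Working it through.** The plan states no figure to reproduce. The check is to follow each rule to the dose it gives.

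**Inputs**

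- Full doses per administration (French 10.1): doxorubicin 25, vinblastine 6 and dacarbazine 375 mg/m², on days 1 and 15, so two doses per cycle.
- Level table and episode actions: French 10.6.1.5.
- Second-episode action: French 10.6.2, multiplier 0.75 on doxorubicin and vinblastine.

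**Under 10.6.2, from full dose**

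- Doxorubicin: 0.75 × 25 = 18.75 mg/m². Vinblastine: 0.75 × 6 = 4.5 mg/m².
- Over the next cycle: 2 × 18.75 = 37.5 and 2 × 4.5 = 9 mg/m².

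**Under 10.6.1.5, by level before the first episode and choice made at that episode**

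| Starting level | First episode | Level after second episode | BV (mg/kg) | AVD | Doxorubicin / vinblastine / dacarbazine (mg/m²) |
|---|---|---|---|---|---|
| 1 | maintain | -1 | 0.9 | full | 25 / 6 / 375 |
| 1 | reduce | -2 | 0.6 | full | 25 / 6 / 375 |
| -1 | maintain | -2 | 0.6 | full | 25 / 6 / 375 |
| -1 | reduce | -3 | 0 | full | 25 / 6 / 375 |
| -2 | maintain | -3 | 0 | full | 25 / 6 / 375 |
| -2 | reduce | -4 | 0 | 0.75 | 18.75 / 4.5 / 281.25 |
| -3 | maintain | -4 | 0 | 0.75 | 18.75 / 4.5 / 281.25 |

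From level -3 with a reduction at the first episode, no lower level remains.

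**Comparison**

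- Starting at level 1, the rules differ whichever choice was made at the first episode: 25 versus 18.75 mg/m² doxorubicin and 6 versus 4.5 mg/m² vinblastine per dose. Over a cycle that is 50 versus 37.5 and 12 versus 9 mg/m².
- From level 1 and with no other reductions, the ladder cannot reach 0.75 AVD before the fourth episode (-1, -2, -3, -4, one step per episode).
- The rules come close only for a participant already at level -2 or -3 before the first episode who reaches -4 at the second. Even then, if 0.75 applies to all three AVD drugs, dacarbazine is 0.75 × 375 = 281.25 mg/m² on the ladder and 375 under 10.6.2.

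**Other differences.** The two texts also differ on prophylaxis (required in all later cycles versus recommended for the next one) and on the third episode (a further level down versus continuing with supportive measures). These can be followed together, so they are secondary.

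**The case against.** The best reconciling reading divides the work. Section 10.6.1.5 sits under 10.6.1, whose heading names only BV, and its first-episode action mentions only the BV dose. Section 10.6.2 gives the vinblastine and doxorubicin rules. A site could step BV down under one and cut doxorubicin and vinblastine under the other. On this view the full-dose entries in the ladder are not absolute, because the Severe Infection and Impaired Hepatic Function rows of 10.6.2 can also cut those drugs, and the Hematologic Toxicity row makes an exception for neutropenic fever when it asks for full AVD on schedule.

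This does not resolve the conflict. Section 10.6.1.5 fixes the AVD dose in its own column, and BV 0.9 mg/kg with 75% doxorubicin and vinblastine is not a level on its ladder. The infection and hepatic rows have different triggers, so their reductions can be added. Here a single trigger carries two different doses.

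Some of the objection stands:

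- The non-hematologic row does name 10.6.1.5 for febrile neutropenia, which reduces the ambiguity. The neutropenia row still points to all of 10.6, which contains both rules.
- A second episode accompanied by grade 3–4 infection from chemotherapy-related neutropenia would still bring a 75% cut through the Severe Infection row. The AMC protocol has the same overlap (5.1.3 and 5.2.4), and the fix leaves it there.
- The 10.6.2 cut is written for the next cycle, with discretionary re-escalation, so the dose difference may last one cycle.
- Adverse event calls between the French and American coordinators and the data monitoring committee may bring a case to light, but neither sets precedence in advance.

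**Conclusion.** The concern holds. For a French participant who has had no earlier reduction for another reason, the second febrile neutropenia episode calls for full-dose AVD under 10.6.1.5 and for 75% doxorubicin and vinblastine under 10.6.2, and the protocol does not say which applies. The size is 6.25 mg/m² of doxorubicin (25 − 18.75) and 1.5 mg/m² of vinblastine (6 − 4.5) per dose.

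The number of participants affected cannot be derived. The documents give no rate of second episodes. The 16% grade 3/4 febrile neutropenia cited in the background comes from 31 patients, of whom only 6 received AVD with BV, so it is not applied here to the 20 planned French participants. The number is probably small. The finding is that the safety dosing instructions contradict each other. It does not say that either rule is unsafe or that the pooled PFS estimate is materially biased.

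**What to change.** Make 10.6.1.5 the governing rule in the French protocol:

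1. Replace the febrile neutropenia row of 10.6.2 with a cross-reference to 10.6.1.5, following AMC 5.2.2.
2. In the neutropenia row of the 10.6.1.2 table, change the pointer from Section 10.6 to Section 10.6.1.5.
3. Leave the Severe Infection row as it is in both protocols, since it has its own trigger.

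Choosing 10.6.1.5 brings the French dosing into line with the AMC ladder, which suits a study whose French and US data are pooled for analysis (French section 16.0). The documents give no reason for a separate French rule.

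The cost is an amendment to one table row and one section pointer, with the ethics committee and competent authority approval that French section 19.10 requires before implementation. Sample size, endpoints and analysis are unchanged.

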- 7. **PFTs** with volumes, spirometry, DLCO and room air pulse oximetry. Patients will be required to obtain a pulmonary function test, despite the exclusion of bleomycin. The DLCO adjusted for hemoglobin must be greater than 70% predicted to enter the study and to continue with brentuximab vedotin.

- 8. **Bone marrow biopsy** for histology and determination of percent bone marrow involvement. If bone marrow involvement by lymphoma has already been documented after bone marrow biopsy performed more than 6 weeks prior to registration, the biopsy does not have to be repeated.
- 9. Central pathology review for confirmation of histology of lymphoma specimen: Biopsy material at diagnosis will be sent to confirm HL and histologic subtype. (See Appendix 20.1 and 20.7 for the acceptable specimens required for central review and for handling instructions).

All specimens will be reviewed by a panel of pathologists and must be submitted within 30 days of study enrollment. Patients who are found not to have HIV-HL will be withdrawn from the study

- 10. Laboratory tests, including:
 - CBC with differential and sedimentation rate (within 2 weeks prior to patient registration).
 - Serum chemistries: electrolytes (Na, K, Cl, bicarbonate, Ca, Mg, and phosphorus), glucose, blood urea nitrogen (BUN), creatinine, total bilirubin, alkaline phosphatase (ALP), LDH, total protein, albumin, AST and ALT (within 2 weeks prior to patient registration).
 - CD4 and CD8 cell count.
 - HIV-1 RNA viral load assessed by any approved viral load assay at the local laboratory. This must be performed within 21 days prior to Cycle 1, Day 1. (The HIV viral load assay must detect at minimum viremia >200 copies/mL to be consistent with the DHHS HIV treatment guidelines).
 - Assessment for Hepatitis C antibody, Hepatitis B core antibody, Hepatitis B surface antigen (HBsAg), and Hepatitis B surface antibody.
 - Serum pregnancy test for women of childbearing potential (within 7 days prior to Cycle 1 chemotherapy). (See Section 13.1.1 under pregnancy and breastfeeding for guidelines on the use of pregnancy category D medications, which includes brentuximab vedotin and dacarbazine.)
- 11. Blood collection for biological analyses (cf. Appendix 20.7) after signature of informed consents for biological and genetic studies.

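### French section 10.6.2, hepatic row: on recovery the prose restores full doxorubicin and vinblastine doses, while the list in the same cell keeps the halved dose

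*Combined protocol and SAP*

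**What the plan says.** The Impaired Hepatic Function row of section 10.6.2 (French protocol) adjusts doxorubicin and vinblastine by direct bilirubin alone. It has a prose part and, below it in the same cell, a three-line list.

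- **Recovery.** Prose: "Full doses should be given once the direct bilirubin is ≤ 2 x ULN". List: "≤ 2 x ULN = 100% of last dose received".
- **Middle band.** The prose condition begins "If the direct bilirubin rises to ≥ 2 x ULN (but ≤ 5 x ULN", and the prose then orders a halving measured from the last dose received. List: "> 2 - 5 x ULN = 50% of last dose received".
- **Top band.** Prose: "If the direct bilirubin rises to ≥ 5 x ULN, doxorubicin and vinblastine should be discontinued for that cycle". The next sentence takes a participant off protocol treatment if direct bilirubin is not back to 2 x ULN or below when the following cycle falls due. List: no dose above 5 x ULN.

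Other rows of the same table state what happens after a cut. Participants with grade 3 vinblastine neuropathy "will have the dose of vinblastine reduced by 50% for all further cycles of AVD". After the 75% step for severe infection, "Re-escalation is at the discretion of the treating physician".

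On measurement, the baseline chemistries in section 9.3 include "total bilirubin, alkaline phosphatase (ALP), LDH, total protein, albumin, AST and ALT (within 2 weeks prior to patient registration". Section 9.4 (item 7) and the flow chart in Appendix 21.2 repeat that panel for days 1 and 15 of each cycle, again naming total bilirubin only. Section 9.4 requires the results before dosing only when there is a clinical reason.

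**The concern.** The prose and the list answer the same question, what to give once direct bilirubin has recovered, and they agree only if the dose was never cut. For a participant who has been reduced, a site working from the list alone would carry the reduced dose forward, because the list contains no step back up. The list is laid out as the quick reference for dose adjustment, so this is a plausible way to use it.

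The neighbouring rows make it harder to dismiss the list as loose wording. Where the table intends a lasting cut, or leaves re-escalation to the physician, it says so. The hepatic list does neither, and nothing in the row says whether prose or list prevails. At stake is a two-fold difference in two cytotoxic doses. A further weakness is that the rule acts on an analyte the visit schedule does not request.

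**Working it through.** No sample size, power or event count is involved, and the row gives no figure to reproduce. The check applies each instruction to one participant.

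**Inputs.** Protocol doses are doxorubicin 25 mg/m² and vinblastine 6 mg/m² on days 1 and 15 (section 10.1). The middle-band step is 0.5 x last dose, in prose and list alike. Recovery is the full dose (prose) or 1.0 x last dose (list).

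**One reduction, then recovery**
- After the reduction: 0.5 x 25 = 12.5 and 0.5 x 6 = 3 mg/m².
- Next dose by the prose: 25 and 6 mg/m².
- Next dose by the list: 1.0 x 12.5 = 12.5 and 1.0 x 3 = 3 mg/m².
- Ratio of list to prose: 12.5/25 = 3/6 = 0.5.

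**Never reduced.** Both give 25 and 6 mg/m², so there is no conflict. The same holds for a participant whose dose was omitted above 5 x ULN straight from full dose.

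**Two in-band results, days 1 and 15 of one cycle**
- Step taken from the last dose (prose and list as written): 12.5, then 0.5 x 12.5 = 6.25 mg/m² doxorubicin; 3, then 0.5 x 3 = 1.5 mg/m² vinblastine. The second dose is 25% of full.
- Step taken from the dose before the hepatic cut: 12.5 and 12.5; 3 and 3 mg/m².

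How far successive halving can go depends on the removal sentence. If it covers the middle band, a participant still in band when the next cycle is due leaves protocol treatment, so at most the two doses of one cycle are affected. If it covers only the step at 5 x ULN, which it directly follows, the row sets no limit.

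**Band edges**
- At exactly 2 x ULN the prose supports both a 50% cut and full dose; the list gives 100% of last dose.
- At exactly 5 x ULN, from full dose, the prose supports both 12.5 and 0 mg/m² doxorubicin; the list gives 12.5 mg/m².

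**Elsewhere in the documents.** The AMC hepatic table (section 5.2.5, Table 5-C) is keyed to total bilirubin and AST. It states percentages without reference to the last dose, so it does not settle the French wording.

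**The case against.** The best defence is that the two lines can be read together. The prose contains the only explicit recovery instruction and probably shows the intent. On that view the list's first line means no hepatic adjustment, and it usefully preserves a cut made for another toxicity, such as the 75% severe-infection step. This is a fair account of what was probably meant. It does not remove the conflict, because the row never says so and the literal list dose is half the prose dose.

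Four stronger readings are tempting, and the documents do not support them.

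- A reader might infer that repeated halving is peculiar to the list. It is not: the prose measures the 50% step from the same base. The prose also speaks of bilirubin rising to the band, so whether a persistent in-band value calls for a second cut is itself a matter of interpretation.
- A reader might infer that doses can fall without limit. The removal sentence may prevent that, depending on its scope.
- A reader might infer that sites cannot apply the rule because direct bilirubin is unavailable. Section 8.1 (item 9) uses it for eligibility, total bilirubin is measured on dosing days, and nothing prevents a site from fractionating it. The gap is in the schedule, not in feasibility.
- A reader might infer that French participants will be underdosed often enough to move the PFS result. No frequency is given, entry criteria already restrict bilirubin, and values must meet eligibility when treatment starts.

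The overlap at exactly 2 or 5 x ULN is minor, and the list's bands already resolve it.

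**Conclusion.** The row is wrong as written and should be corrected. After one 50% hepatic reduction and recovery, prose and list differ by a factor of two: 25 versus 12.5 mg/m² doxorubicin and 6 versus 3 mg/m² vinblastine. Separately, the shared base for the 50% step leaves room for a further halving, to 6.25 and 1.5 mg/m², on a second in-band result before recovery. The trigger for the whole row is missing from the scheduled chemistries.

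The two-fold figure assumes a participant at full dose with a single hepatic cut and a site that follows the list literally. The point reaches only French participants, 20 of the 51 planned (section 7.0), and among them only those reduced for direct bilirubin who then recover or stay in band. It is a dosing-instruction defect; it touches neither the sample size nor the analysis, and no effect on the PFS estimate is claimed.

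**What to change.** Amend the French hepatic row and the chemistry list as follows.

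1. Define the reference dose as the dose in force before the hepatic reduction. Cuts for other toxicities are then kept: after a 75% severe-infection step the reference is 0.75 x 25 = 18.75 mg/m² doxorubicin and 0.75 x 6 = 4.5 mg/m² vinblastine.
2. Change the first list line so that recovery to 2 x ULN or below restores that reference dose, and word the prose recovery sentence to match.
3. State in both prose and list that the 50% step is taken from the same reference dose. Repeated in-band results then no longer compound, whatever the scope of the removal sentence.
4. Use the list's bands in the prose: ≤ 2, > 2 to 5, and > 5 x ULN.
5. Add direct bilirubin to the day 1 and day 15 chemistries in section 9.4 and Appendix 21.2, run on the sample already drawn.

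The cost is a wording amendment to one row and one added analyte, with a small laboratory charge. There is no extra visit or blood draw, and no change to sample size or analysis.
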